8. STUDY PROCEDURES

8.1 Study Design

This is a Phase II, prospective, multicenter, randomized, single-masked, sham-controlled study to assess the safety, tolerability and evidence of activity of multiple IVT injections of APL-2 in subjects with GA associated with Age-Related Macular Degeneration.

Patients diagnosed with GA associated with age-related macular degeneration in the study eye and who meet all inclusion/exclusion criteria will be included in the study. The study will randomize approximately 240 subjects to obtain at least 200 evaluable subjects across 40 multinational sites.

Patients should be screened 14 (\pm 5) days before receiving APL-2. Upon entry into the study, patients will be assigned a subject screening number. Subjects who meet all inclusion and exclusion criteria and are confirmed as eligible by the CRC will return to the clinic for the randomization visit (Day 0) and randomized as outlined in [Section 7.1](#).

All subjects will return to the clinical site on Day 7 to assess acute safety after the first injection. After that, subjects in the monthly groups will return to the clinical site for additional APL-2 (or

[figure not shown]

Sham) injections and study procedures every month until Month 12. Subjects in the EOM groups will return to the clinical site for additional APL-2 (or Sham) injections and study procedures every two months until Month 12. All subjects will return for follow-up visits 3 and 6 months after Month 12 (Months 15 and 18, respectively)

Subjects who discontinue study treatment, can continue participation in the study and return to the clinical site for their scheduled study procedures (with the exception of APL-2/Sham administration).

Subjects who fully withdraw from the study before Month 12, should complete the Termination Visit.

See Study Outline below.

AM = APL-2 Monthly. SM = Sham Monthly. AEOM = APL-2 Every-Other-Month. SEOM = Sham Every-Other-Month. D = Day. M = Month.
 SMC = Safety Monitoring Committee. SMC will review cumulative safety data after the first 20 subjects have completed Day 7, Month 2 and Month 6 visits.
 * Eligibility to be confirmed by Central Reading Center.

Safety will be assessed throughout the study; serial blood samples and urine samples will be collected. Blood samples will also be collected for the PK assessment of APL-2.

The planned length of participation in the study for each subject is approximately 18.5 months (from Day –14 through completion of the Month 18 (Day 540) follow-up procedures).

The study is planned to take place over approximately 28 months (from screening of the first subject through completion of the last subject’s exit visit).

8.2 Safety Monitoring Committee

An external, independent Safety Monitoring Committee (SMC) will review cumulative unmasked safety data and will have the responsibility to conduct a thorough safety assessment after the first 20 subjects have completed the Day 7, Month 2 and Month 6 visits. A key responsibility of the SMC will be to make a recommendation whether to continue, modify or stop the study based upon an evaluation of emerging safety data, in particular Adverse Events of Special Interest as outlined in [Section 10.1.3](#). Additional regular or ad-hoc safety reviews will be scheduled as recommended by the SMC.

8.3 Study Visit Schedule

Below is a condensed description of the study visits and the procedures and examinations that will be performed. Please refer to the Study Flow Charts in [Section 2](#) for a detailed schedule of procedures/assessments for the Monthly and EOM visit schedules. Additional safety assessments not listed in section 8.3 or the flow chart may be performed if considered necessary at the discretion of the PI.

8.3.1 Screening – Within 14 days prior to treatment

Visit 1 - All subjects

All ophthalmic procedures (including imaging) are to be performed on **both eyes**

1. Before any study specific procedures are performed, explain the purpose and nature of the study, and have the patient read, sign, and date the Institutional Review Board/Independent Ethics Committee (IRB/IEC)-approved Informed Consent Form (ICF). Have the individual obtaining consent from the patient and a witness, if applicable, sign and date the ICF.
2. Obtain a screening number for the subject.
3. Obtain information on demographics, medical/ocular history, and concomitant medications used 90 days prior to enrollment. Include vitamins, and all over-the-counter as well as prescription medications.
4. Screen the patient for inclusion/exclusion criteria.
5. Collect blood (including blood for HCG/FSH/LH, if applicable) and urine for laboratory analysis and forward the samples to the central laboratory.
6. Collect blood for PK and anti-APL-2 antibody analysis.
7. Collect vital signs.
8. Perform BCVA.
9. Perform LL-BCVA.
10. Perform a complete ophthalmic exam including slit-lamp exam of the cornea, iris, anterior chamber, lens (LOCS III if any opacity on the lens noted) and aqueous reaction (cells and flare), dilated fundus exam of the vitreous and retina and IOP measurement.
11. Perform SD-OCT imaging and forward the images to the CRC for determination of eligibility.
12. Perform FAF imaging and forward the images to the CRC for determination of eligibility.
13. Perform IR imaging (if applicable) and forward the images to the CRC.
14. Perform DCFP and forward images to the CRC for determination of eligibility.
15. Perform FA and forward the images to the CRC for determination of eligibility.

8.3.2 Initial Treatment – Day 0 – Within 14 Days of screening

Visit 2 – All groups

Unless specified, all ophthalmic procedures (including imaging) are to be performed on the **study eye only**.

1. Verify that all inclusion/exclusion criteria are met, including the determination of eligibility by the CRC.
2. Obtain information on any changes in medical health and/or the use of concomitant medications.
3. Collect vital signs pre- and post-dose. Vital signs will be measured within approximately 1 hour prior to dosing for the pre-dose time point. Post-dose vital signs readings will be performed within 30 minutes after dosing.
4. Perform BCVA.
5. Perform LL-BCVA.
6. Perform a complete ophthalmic exam including slit-lamp exam of the cornea, iris, anterior chamber, lens (LOCS III if any opacity on the lens noted) and aqueous reaction (cells and flare), dilated fundus exam of the vitreous and retina and IOP measurement.
7. Use Interactive Web Response (IWR) for subject randomization
8. Perform the IVT injection of APL-2 (or Sham injection) as described in the MOP.
9. Monitor the study eye within 15 minutes post injection as outlined in [Section 9.8](#) and in the MOP.
10. Monitor for adverse events.

8.3.3 Post initial treatment examination - Day 7 –

Visit 3 – All groups

Unless specified, all ophthalmic procedures (including imaging) are to be performed on the **study eye only**.

1. Obtain information on any changes in medical health and/or the use of concomitant medications.
2. Collect vital signs.
3. Collect blood for PK analysis.
4. Perform BCVA.
5. Perform LL-BCVA.
6. Perform a complete ophthalmic exam including slit-lamp exam of the cornea, iris, anterior chamber, lens (LOCS III if any opacity on the lens noted) and aqueous reaction (cells and flare), dilated fundus exam of the vitreous and retina and IOP measurement.

7. Monitor for adverse events.

8.3.4 Injection Visits – Monthly or EOM until month 12 -

Monthly Groups: Days 30, 60, 90, 120, 150, 180, 210, 240, 270, 300, 330 and 360 - Visits 4, 5, 6, 7, 8, 9, 10, 11, 12, 13, 14 and 15, respectively.

EOM Groups: Days 60, 120, 180, 240, 300 and 360 – Visits 4, 5, 6, 7, 8 and 9 respectively.

Unless specified, all ophthalmic procedures (including imaging) are to be performed on the **study eye only**. The following procedures will be performed at all injection visits:

1. Obtain information on any changes in medical health and/or the use of concomitant medications.
2. Collect vital signs pre- and post-dose. Vital signs will be measured within approximately 1 hour prior to dosing for the pre-dose time point. Post-dose vital signs readings will be performed within 30 minutes after dosing.
3. Collect blood for PK analysis.
4. Perform urine pregnancy test before APL-2 injection. **-WOCBP only-**
5. Perform BCVA. **-Both eyes on Day 360 only-**
6. Perform LL-BCVA. **-Both eyes on Day 360 only-**
7. Perform a complete ophthalmic exam including slit-lamp exam of the cornea, iris, anterior chamber, lens (LOCS III if any opacity on the lens noted) and aqueous reaction (cells and flare), dilated fundus exam of the vitreous and retina and IOP measurement.
8. Perform the IVT injection of APL-2 (or Sham injection) as described in the MOP.
9. Monitor the study eye within 15 minutes post-injection as outlined in [Section 9.8](#) and in the MOP.
10. Monitor for adverse events.

The following procedures will be performed only at specific visits, as noted:

1. Collect blood and urine for laboratory analysis and forward the samples to the central laboratory. - **Only on Days 60, 180 and 360 for all groups -**
2. Collect blood for genetic marker analysis (if applicable, see [Section 9.3](#)) and forward the samples to the central laboratory. - **Only on Days 60 for all groups -**
3. Perform SD-OCT imaging and forward the images to the CRC. - **Only on Days 60, 180 and 360 for all groups -**
4. Perform FAF imaging **of both eyes** and forward the images to the CRC. - **Only on Days 60, 180 and 360 for all groups -**
5. Perform IR imaging (if applicable) **of both eyes** and forward the images to the CRC. - **Only on Days 60, 180 and 360 for all groups -**

8.3.5 Follow up visit - Day 450 -

Visit 16 and 10 for Monthly and EOM, respectively

Unless specified, all ophthalmic procedures are to be performed on the **study eye only**.

1. Obtain information on any changes in medical health and/or the use of concomitant medications.
2. Collect blood for PK analysis.
3. Collect vital signs.
4. Perform urine pregnancy test. **-WOCBP only-**
5. Perform BCVA.
6. Perform LL-BCVA.
7. Perform a complete ophthalmic exam including slit-lamp exam of the cornea, iris, anterior chamber, lens (LOCS III if any opacity on the lens noted) and aqueous reaction (cells and flare), dilated fundus exam of the vitreous and retina and IOP measurement.
8. Monitor for adverse events.

8.3.6 Termination Visit (or Early Termination) – Day 540 -

All ophthalmic procedures are to be performed on **BOTH EYES**.

1. Obtain information on any changes in medical health and/or the use of concomitant medications.
2. Collect blood and urine for laboratory analysis and forward the samples to the central laboratory.
3. Collect blood for PK analysis.
4. Collect vital signs.
5. Perform urine pregnancy test. **-WOCBP only-**
6. Perform BCVA.
7. Perform a complete ophthalmic exam including slit-lamp exam of the cornea, iris, anterior chamber, lens (LOCS III if any opacity on the lens noted) and aqueous reaction (cells and flare), dilated fundus exam of the vitreous and retina and IOP measurement.
8. Perform SD-OCT imaging and forward the images to the CRC.
9. Perform FAF imaging and forward the images to the CRC
10. Perform IR imaging (if applicable) and forward the images to the CRC.
11. Perform DCFP imaging and forward images to the CRC.
12. Perform FA imaging and forward the images to the CRC.
13. Monitor for adverse events.

8.3.7 Unscheduled Visit

If a subject returns to the clinical site before their next scheduled visit for an assessment of an adverse event or at the request of the PI, all assessments completed at the Unscheduled Visit should be documented in the patient source record and in the eCRF.

9. ASSESSMENTS

The following evaluations will be performed during the study as outlined in the Study Flow Charts in [Section 2](#). Refer to the MOP for detailed descriptions of study-related procedures.

9.1 Vital signs

Vital signs consist of body temperature, respiratory rate, blood pressure, and heart rate measurements. Standardized procedures for each are provided in the MOP.

On injection visits, vital signs will be measured within approximately 1 hour prior to dosing and within 30 minutes after dosing.

Vital signs will be measured before venipuncture.

9.2 Laboratory analysis of blood and urine

Collection of blood and urine will occur at the study site and the samples will be shipped to a central laboratory for analysis. A standardized procedure for the collection and processing of blood and urine is provided in the MOP.

The following clinical labs will be performed:

Hematology

- Hemoglobin
- Hematocrit
- Red blood cell (RBC) count
- Platelet count
- White blood cell (WBC) count with differential

Chemistry

- Blood urea nitrogen (BUN)
- Creatinine
- Bilirubin (total, direct and indirect)
- Albumin
- Alkaline phosphatase (ALP)
- Aspartate aminotransferase (AST)
- Alanine aminotransferase (ALT)
- Creatine kinase
- Glucose
- Electrolytes (sodium, potassium, chloride, bicarbonate)

Urinalysis

- pH
- Specific gravity
- Protein
- Glucose
- Ketones
- Bilirubin
- Blood
- Nitrite
- Urobilinogen
- Leukocyte esterase

Complement

- C3
- CH50

Other

- Human chorionic gonadotropin (HCG) ^a
- Follicle-stimulating hormone (FSH) ^b
- Luteinizing hormone (LH) ^b

The Investigator must review the results of the Screening Visit clinical laboratory tests (including recheck results) and confirm that these results do not show evidence of any medical condition that would make study participation inappropriate. The Investigator should also assess any changes from baseline at the follow up visits and the Exit Visit.

Notes:

- Serum Pregnancy Test (i.e. HCG) will be performed for females of child bearing potential at screening only.
- FSH and LH will be performed for postmenopausal females at screening only.

9.3 Genotyping Samples

The genetic marker sample will be used to evaluate the relationship between genetic polymorphisms associated with AMD with disease progression and response to APL-2.

A whole-blood sample will be collected for genetic marker analysis at the Day 60 visit. These samples will be required for all subjects with the exemption of clinical sites located where prohibited by law, clinical sites with policies in place that prohibit collection of samples for genetic marker testing and clinical sites where IRB/IEC has not approved genetic testing.

9.4 Urine pregnancy test

Urine pregnancy test will be performed in WOCBP only as outlined in the Study Flow Chart in [Section 2](#).

9.5 Best-corrected visual acuity

Best-corrected visual acuity (including LL-BCVA) testing, performed by a certified VA examiner, should precede any examination requiring administration of eye drops to dilate the eye or any examination requiring contact with the eye. Best-corrected visual acuity should be performed following refraction and completed according to the procedures outlined in the MOP.

9.6 Complete ophthalmic exam

The complete ophthalmic exam will consist of the following:

- External examination of the eye and adnexa.
- Routine screening for eyelids/pupil responsiveness (including ptosis, abnormal pupil shape, unequal pupils, abnormal reaction to light and afferent pupillary defect).
- Slit-lamp examination [cornea, anterior chamber, iris, lens, aqueous reaction (cells and flare). Grading scales are outlined in the MOP. If an abnormal lens finding is noted during

the slit-lamp examination, at any visit, then the finding should be further characterized with LOCS III. All subsequent visits for that subject should include LOCS III. A complete description of LOCS III standardized procedures and grading scales is outlined in the MOP.

- Dilated fundus exam including evaluation of retina and vitreous (i.e. posterior segment abnormalities, retinal hemorrhage/detachment, and vitreal hemorrhage density and vitreous cells). Vitreal hemorrhage density and vitreous cells grading scales are outlined in the Manual of Procedures.
- IOP measurement - A measurement of intraocular pressure will be conducted using Tonopen, iCare or Goldmann applanation tonometer as outlined in the MOP. The same method should be used for all measurements in the same subject throughout the study.

9.7 Ocular Imaging

The following ocular images will be obtained and sent to the CRC as outlined in the visit schedule in [Section 8.3](#). Also see Study Flow Charts in [Section 2](#).

- Digital Color Fundus Photographs
- Fluorescein angiography
- Spectral Domain Optical coherence tomography
- Fundus Autofluorescence
- Infrared reflectance imaging. Only done at selected clinical sites with Heidelberg Spectralis® system.

A standardized procedure for the collection of each imaging modality is provided in the CRC manual/s. Certification of the equipment and examiners for all imaging modalities at each investigative site will occur prior to any evaluation of study subjects.

9.8 Post-injection assessment

The study eye will be assessed before and after injection to ensure that the injection procedure and/or the study medication have not endangered the health of the eye. The initial post-injection assessments should be done within 15 minutes post-injection and include a gross assessment of vision (light perception) and monitoring IOP. If subject passes gross vision test and IOP is < 30 mmHg, the subject may leave the site. If subject fails gross vision test **and/or** IOP is > 30 mmHg, assessments will continue every approximately 30 minutes until the subject passes gross vision test and IOP is < 30 mmHg. Any subject who develops a significant and sustained raise in IOP (> 30 mmHg) or a non-adequately perfused central retinal artery (CRA) after any APL-2 injection, should be monitored according to the PI's clinical judgment and may undergo additional procedures and measurements of IOP beyond those specified in the protocol as well as IOP lowering procedures. If any concern or immediate toxicity is noted, the subject will remain at the site and will be treated according to the PI's clinical judgment.

9.9 Blood Volume for Study Assessments

Blood Volume during Study (up to Day 113)

Assay	Number of Time Points	Approximate Volume per Time Point * (mL)	Approximate Sample Volume Over Course of Study (mL)
Pharmacokinetics	10/16	4	40/64
Anti-APL-2 Antibodies	10/16	4	40/64
Hematology	5	4	20
Chemistry (Incl. HCG/LH/FSH)	5	8.5	42.5
Genotyping Sample	1	2	2
Complement profile (C3, CH50 and Total complement)	4	4	16

Total Blood Volume for Study 160.5/208.5

Note: Number of samples (and volumes) for certain assays differ for Monthly vs EOM groups and are expressed as M/EOM.

10. ADVERSE EVENTS

All adverse events (AEs) (as defined in [Section 10.1](#)), either observed by the PI or one of their medical collaborators, or reported by the participant spontaneously, or in response to direct questioning, will be reported. All adverse events (ocular, non-ocular, serious, non-serious, volunteered, and elicited) must be documented in study records.

10.1 Definitions

10.1.1 Adverse Event

An adverse event is any untoward medical occurrence in a subject who receives a pharmaceutical product. The occurrence does not necessarily have to have a causal relationship with the treatment. Therefore, an AE can be any unfavorable and unintended sign, symptom, or disease temporally associated with the use of a drug, whether or not considered related to the drug.

Note:

- For purposes of this study, abnormal laboratory values will not be considered adverse events unless deemed clinically significant by the Investigator. All abnormal laboratory values will be recorded in the database and appropriate analyses presented in the final study report.

10.1.2 Serious Adverse Event

A serious adverse event (SAE) is defined as any untoward medical occurrence that at any dose:

- Results in death;
- Is life-threatening: this means that the subject was at risk of death at the time of the event; it does not mean that the event might have caused death had it occurred in a more severe form;
- Required hospitalization or prolongation of existing hospitalization;

- Results in persistent or significant incapacity or substantial disruption of the ability to conduct normal life functions; or
- Is a congenital anomaly or birth defect

Important medical events that may not result in death, be life-threatening, or require hospitalization may be considered serious when, based upon appropriate medical judgment, they may jeopardize the patient or subject and may require medical or surgical intervention to prevent one of the outcomes listed in the above definition.

Medical and scientific judgment should be exercised in deciding if an AE is serious and if expedited reporting is appropriate.

10.1.3 Adverse Events of Special Interest

An adverse event of special interest is one of scientific and medical concern specific to the Sponsor's product or program where ongoing monitoring and rapid communication by the Investigator to the Sponsor may be appropriate. These adverse events may be serious or non-serious. Applicable adverse events may require further investigation in order to characterize and understand them, and depending upon the nature of the event, rapid communication by the trial Sponsor to other parties may also be required. These adverse events of special interest must be reported using the same mechanism and timeframe (i.e. within one working day of the Investigator's or delegate's knowledge of the event) as described for serious adverse events in [Section 10.3](#). The adverse events of special interest include the following:

- Endophthalmitis
- 4+ ocular inflammation
- 2-3+ ocular inflammation that fails to decrease to 1+ or less within 30 days of the onset of the event
- Sustained (> 5 minutes) loss of light perception after APL-2 injection
- Sustained elevation of IOP (30 mmHg) at/past 90 minutes post-injection
- Any elevation of IOP requiring surgical intervention (i.e. paracentesis)
- New vitreous hemorrhage of > 2+ severity that does not resolve within 14 days of the onset of the event
- Progression to exudative AMD in the study eye or fellow eye requiring **surgical** intervention (see note below).

If an adverse event of special interest occurs in a study subject, the study subject will be followed for resolution of the adverse event. A decision will be made by the Sponsor concerning further exposure to the study treatment and further participation in the study.

Note: Intravitreal administration of anti-VEGF agents are **not** considered surgical interventions.

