7.2 Masking and Minimization of Bias

The intent of masking is to limit the occurrence of conscious and unconscious bias in the conduct and interpretation of the clinical study. Bias could arise from the influence that the knowledge of a specific treatment assignment may have on the recruitment and allocation of subjects, their subsequent care, the assessment of end points, the handling of withdrawals, and so on. The essential aim of masking, therefore, is to prevent identification of the treatments by the subject and the masked assessors associated with the conduct of the study until all such opportunities for bias have passed.

This single-masked study is subject-masked and assessor masked, with subjects randomized to either APL-2 or Sham Injection, as well as to a monthly or EOM treatment schedule for 12 months. To prevent bias in treatment assignment, eligible patients will be randomized using a web-based randomization system. The subject and assessors (photographer(s) and visual acuity technicians) will be masked to the specific treatment being administered. The Investigators (including Sub-Investigators), site personnel not performing assessments of efficacy variables (imaging and visual acuity), vendors and Sponsor (or Contract Research Organization (CRO)) personnel will be unmasked to treatment assignment. Additionally, a masked independent review of SD-OCT, FAF, DCFP and FA images will be performed at the CRC to provide an objective assessment of these evaluations.

This level of masking will be maintained throughout the conduct of the study. In the event of a medical emergency where the knowledge of subject treatment by masked individuals (e.g. the subject or his/her physician) is required, an individual Investigator will have the ability to unmask the treatment assignment for a specific subject and share that information with the appropriate parties. The Investigator must endeavor to notify the Sponsor prior to unmasking a subject. The independent SMC will be provided unmasked safety data for their safety assessment.

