7.3.3 Intravitreal APL-2 Administration

Subjects receiving active treatment will be administered a 100 µL IVT injections of APL-2 using a 29G or 27G thin wall needle, at the discretion of the PI. Detailed instructions on drug preparation, pre-injection procedures, administration of APL-2, and post-injection procedures are provided in the MOP. The procedure for sham injection will be the same as that used for IVT injection until the actual injection; no actual injection will occur. Detailed instructions on sham injection procedures are provided in the MOP.

Clinic staff involved in the injection tray assembly, anesthetic preparation, and study drug preparation and administration will follow appropriate aseptic techniques to minimize the risk of potential adverse events associated with IVT injections (e.g. endophthalmitis).

To minimize IOP elevation after IVT injection of APL-2, decompression of the eye must be performed before all APL-2 injections. This is done by applying moderate pressure to the globe with cotton swabs for 30-60 seconds during anesthetic preparation.³¹

In addition to the procedures outlined in the MOP, adherence to specific institutional policies associated with IVT injections will be observed.

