10.3 Serious Adverse Event Reporting

All SAEs (defined in [Section 10.1.2](#)), whether judged related or not to study medication, will be reported to the Sponsor (or designated Medical Monitor) by telephone, e-mail or facsimile within

24 hours of the Investigator becoming aware of such SAEs. Contact information and instructions for completing SAE forms are provided in the MOP.

The initial SAE Report should include, at a minimum, the following information:

- Protocol number (POT-CP121614)
- Site number
- Subject screening number, initials, gender, and date of birth
- Name of PI and investigator site address
- Details of SAE
- Criterion for classification as “serious”
- Date of SAE onset

Follow-up SAE reports should be submitted as further information becomes available, and the final SAE Report should include information on the SAE intensity, outcome, and relationship to study drug; dates of study drug administration, concomitant medications, and any other relevant information. The PI should also provide clear copies of supporting documents as necessary (e.g. hospital discharge summary, laboratory reports, autopsy reports, etc), with the subject’s personal identifiers removed. All SAEs will be followed until the acute event has resolved, even if the subject discontinues study participation prior to the resolution. The Investigator must report SAEs occurring at his/her site to the IRB/IEC as required.

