10.5.1 Withdrawal

Participants may choose to discontinue from treatment or to completely withdraw from this study for any reason at any time without penalty or prohibition from enrolling in other clinical protocols.

Participants wishing to withdraw from the study completely will be offered an early termination visit. This early termination visit will include the examinations outlined in [Section 8.3.6](#).

Participants wishing to discontinue treatment but willing to continue with other study procedures, will return to the clinical site for follow-up visits, as per protocol, every month or every two months until Month 12 and then Month 15, and a Termination Visit at Month 18.

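### Protocol 10.1.3 lets the unmasked Sponsor end a subject's study participation, not only treatment, after an adverse event of special interest, with no stated criteria

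*Protocol*

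**What the plan says.** Protocol 10.1.3 makes two statements about a subject who has an AESI. First, "the study subject will be followed for resolution of the adverse event". Second, "A decision will be made by the Sponsor concerning further exposure to the study treatment and further participation in the study". No criteria for that decision appear there or elsewhere in the Protocol or SAP.

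The surrounding provisions are:

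- **Masking.** Protocol 7.2: "vendors and Sponsor (or Contract Research Organization (CRO)) personnel will be unmasked to treatment assignment". SAP 3.4 agrees.
- **Stopping treatment.** Protocol 8.1: "Subjects who discontinue study treatment, can continue participation in the study and return to the clinical site for their scheduled study procedures". Protocol 10.5.1: "Participants wishing to discontinue treatment but willing to continue with other study procedures, will return to the clinical site for follow-up visits".
- **Leaving the study.** Under Protocol 8.1, subjects who fully withdraw before Month 12 should have a Termination Visit; 10.5.1 says it is offered to participants who wish to withdraw. Its content (8.3.6) covers both eyes and includes BCVA, FAF, SD-OCT, fluorescein angiography, laboratory tests and AE review.
- **Safety data after leaving.** Under Protocol 11.4, AE collection ends on completion or premature discontinuation. Under 10.3, SAEs are followed until the acute event resolves, "even if the subject discontinues study participation prior to the resolution".
- **Independent oversight.** The task of the Safety Monitoring Committee (SMC) under Protocol 8.2 is to "make a recommendation whether to continue, modify or stop the study", which is a study-level role.
- **Analysis.** SAP 6.1 includes assessments made after treatment stops. The primary analysis is an MMRM that assumes data are missing at random (SAP 6.2.1, 8.1).

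**The concern.** The clause ties together two decisions that need different safeguards. Stopping injections after an AESI is a matter of subject protection. Ending participation also decides whose later outcomes are recorded, and here a party that knows the arm may make that decision without criteria and without independent review of the individual case.

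Two things are at stake. The first is safety information. TEAEs are the primary safety endpoint, and 10.1.3 itself describes AESIs as events that may need further investigation. Later events in the same eye, such as a retinal detachment or ocular surgery (both secondary safety endpoints), could follow resolution of the index event and go unrecorded. The second is the balance of follow-up between arms: if removals fall mainly on APL-2, Month 12 FAF values go missing mainly from APL-2.

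**Working it through.** **1. Do other clauses limit the Sponsor's decision?** They do not. Section 8.1 says that a subject off treatment may stay, and 10.5.1 starts from the participant's wish. Both make off-treatment follow-up available, but neither binds the Sponsor. The SMC advises on the study as a whole.

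**2. What follow-up is left after removal?** Follow-up to resolution of the event (10.1.3; 10.3 for SAEs) and, before Month 12, one Termination Visit. Scheduled visits forgone, from the flow charts in Protocol section 2:

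| Removal point | Monthly arms | EOM arms | FAF visits lost |
|---|---|---|---|
| After Month 6 | Months 7, 8, 9, 10, 11, 12, 15, 18 = 8 | Months 8, 10, 12, 15, 18 = 5 | Months 12 and 18 = 2 |
| After Month 12 | Months 15, 18 = 2 | Months 15, 18 = 2 | Month 18 = 1 |

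**3. Which arms?** Protocol 4.3 names endophthalmitis, haemorrhage and raised IOP as risks of intravitreal injection. For sham, "no actual injection will occur" (7.3.3). Most items on the AESI list are of this kind. The exception is exudation needing surgery, which can arise in any arm.

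**4. How would removal reach the primary analysis?** The Month 12 window is Days 347 to 376 (SAP 6.3, Table 2) and applies to the assessment date. An exit FAF outside it does not count as Month 12 in the MMRM, but can be the last observation in the LOCF sensitivity analysis (SAP 6.2.1, 8.1.1). An exit FAF inside the window, after a late removal, does count.

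**5. How large could the efficacy effect be?**

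*Choice of SD.* Protocol 11.3.3 gives power of 91%, 91% and 83% for three scenarios with 67 per group. A one-way ANOVA has noncentrality λ = n Σ(μᵢ − μ̄)²/σ², with 2 and 198 degrees of freedom and alpha 0.10.

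- Means 0.23, 0.23, 0.33 (or 0.23, 0.33, 0.33) and σ = 0.20: λ = 67 × 0.00667/0.04 = 11.2, power 91.4%.
- Means 0.23, 0.28, 0.33: λ = 67 × 0.005/0.04 = 8.4, power 82.6%.
- With σ = 0.21 the figures are 88.8%, 88.8% and 79.0%, which do not match.

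So 0.20 is the value behind the plan's power, as SAP 13 (item 5) states. I use it below.

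*Standard error of an arm difference:* 0.20 × √(2/67) = 0.0346 mm.

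*Assumptions, not in the documents:* 1% to 10% of an APL-2 arm is removed (about 1 to 8 of 80), and growth returns to the untreated rate. The departure over a full year is then 0.33 − 0.23 = 0.10 mm. If treatment stops at Month 6 it is 0.10 × 6/12 = 0.05 mm.

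*Shift in arm mean = fraction removed × departure:*

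| Departure | 1% removed | 10% removed |
|---|---|---|
| 0.10 mm | 0.001 mm (0.03 SE) | 0.010 mm (0.29 SE) |
| 0.05 mm | 0.0005 mm (0.01 SE) | 0.005 mm (0.14 SE) |

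The shift would favour APL-2, because the model would treat the removed subjects' growth as similar to that of comparable subjects who stayed. It scales in proportion if the departure is larger, but that would need growth faster than the untreated rate.

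*Power.* The dropout allowance is 80 − 67 = 13 per arm (16%), so 1 to 8 removals may fit within it.

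**The case against.** The best defence is that the plan already leans towards retention. Sections 8.1 and 10.5.1 provide for off-treatment visits, SAP 6.1 uses the data, and the Sponsor's decision can just as well be to keep the subject in the study. SAP 7.1 tabulates withdrawal reasons by arm, and the unmasked SMC looks at AESIs in particular. All of this is true. It makes the practical risk small, but it does not take away the power that 10.1.3 gives.

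Several stronger readings are tempting, and the documents do not support them:

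- **That follow-up simply ends at resolution.** This leaves out the Termination Visit, which is a full examination with FAF. It is still a single visit, worded for subjects who withdraw, and it does not replace Months 12 and 18.
- **That retention would secure a Month 12 value.** Endophthalmitis, severe inflammation or persistent vitreous haemorrhage may make FAF ungradable. Retention makes a value more likely but cannot guarantee it.
- **That the clause explains or hides the exudation imbalance in Protocol 4.3.** Exudation treated with anti-VEGF is not an AESI; only exudation needing surgery is.
- **That the missing-at-random assumption is a defect of this clause.** The assumption applies to all dropout, including the 15–20% already planned for. It is true that no listed sensitivity analysis assumes faster growth after a subject leaves, but that point is general and adds no weight here.

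**Conclusion.** The point holds as a minor one. The text of 10.1.3 gives an unmasked party discretion, without criteria, over who stays in the study after an AESI, and no other clause restricts it. The firm part of the size is the number of visits left unprotected: up to 8 or 5 per subject removed after Month 6.

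The efficacy part rests on assumed removal rates and is probably negligible, at most about 0.29 SE even at 10% removed and the full-year departure. AESIs have high thresholds, and nothing in the documents points to a rate near 10%. No loss of power is claimed. A reader might infer that the primary result is biased or that subjects were in fact removed; neither document shows either. The case for change therefore rests on complete safety follow-up after AESIs and on keeping unmasked discretion out of retention.

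**What to change.** In Protocol 10.1.3, limit the Sponsor's decision to further study treatment. Add that subjects who remain willing continue all scheduled FAF and safety visits to Month 18 unless they withdraw. Subject protection does not depend on removal, since dosing can still be stopped (13.10 also gives the investigator that right). Optionally, record a Sponsor decision after an AESI as its own withdrawal reason in the SAP 7.1 table.

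The change adds no visits beyond those scheduled and no new analysis. Its costs are a protocol amendment with IRB/IEC approval (13.5), possibly re-consent (12.3), and the Sponsor's loss of discretion to end follow-up of a willing subject. Timing matters: an amendment made after Month 12 cannot recover Month 12 FAF and protects only the Month 15 and Month 18 visits, with one FAF.
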